 - i. A blood sample for dengue, *Zika* and/or *chikungunya* diagnosis and for haematology (CBC and HCT) (**mandated procedure for subjects presenting within the first 14 days following onset of fever and/or rash**) will be collected at the first visit for suspected dengue, *Zika* and/or *chikungunya* (acute blood sample) and
 - ii. a second blood sample (convalescent blood sample) will be collected approximately 21 (maximum 28 days) days later.
 - iii. In between, a return visit may be scheduled as needed.
- **Data collection:** eCRF
- **Type of study:** self-contained

- **Duration of the study:** Four years for the overall study. For an individual subject, it will range between one and four years.
 - **Epoch 001:** prospective data collection starting at Visit 1 Day 0 and ending at the last subject last visit.

Synopsis Table 1 Study group and epoch foreseen in the study

Study Group	Number of subjects*	Age (Min/Max)	Epoch
Prospective study cohort	Initial Cohort: 1800 at enrolment (first year) At least 1500 in each subsequent year	6 months of age and older	Epoch 001
	Expansion Cohort: 1800 at enrolment (first year). At least 1500 in each subsequent year		

* The final number of participants will take into account the active subjects, subjects who prematurely terminate participation and subjects lost to follow-up.

Discussion Selection of study sites of study design

At least six sites in Brazil will be selected for this study. Selection criteria include support from the Family Health Physician Program (FHP), the Larval Index Rapid Assay (LIRA) or with field research experience in the community. The FHP is a Brazilian government public health strategy that consists of multidisciplinary teams of health care workers that cover geographically defined areas to provide basic/preventive care to community members. The teams include a doctor, a nurse, a nurse auxiliary, other health professionals and community health care workers who pay regular visits to the household under its responsibility to deliver health promotion activities and facilitate triage and referral into the health unit, among other activities. Community health care workers are local residents who are trained for basic tasks.

LIRA is an alternative vector surveillance strategy that consists of random sampling of a number of dwellings in which surveillance of aedes-positive breeding places is carried out, and has been widely implemented in Brazil (Pontes, 2000).

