Blood sample for dengue/zika/chikungunya infection differential diagnosis ³												•		•
Blood sample for CBC and hematocrit (mandated for subjects presenting within 14 days following symptoms⁶ onset)												•		
Record body temperature												•		
Report SAEs related to study procedures ⁴	•		•		•		•		•		•	•	•	•
Collect or verify diary logs if applicable												0	0	0
Study conclusion ⁵												•		•

CONFIDENTIAL

116606 (EPI-DENGUE-006 BOD BR)
Protocol Amendment 4 Final

- is used to indicate a study procedure that requires documentation in the individual eCRF.
- is used to indicate a study procedure that does not require documentation in the individual eCRF.

¹ Diary logs given at scheduled visits are only to be filled out in the event that the subject has fever **and/or rash according to the case definition for** suspected dengue/**chikungunya/Zika**. See Section 5.5.2.5 for details with regard to the diary log.

² A return visit is a visit linked to suspected dengue/**chikungunya/Zika**, occurring if the evolution of the subject's physical condition necessitates medical evaluation, according to local medical practice. The investigator will determine whether this return visit is necessary and whether it is considered as part of the same episode. See Section 5.6 for details.

³ **Blood sampling for dengue diagnosis which includes** testing for RT-qPCR, dengue IgG and IgM ELISA, NS1 ELISA, neutralizing antibodies to dengue and **virological/humoral, testing for Zika and chikungunya infection.**

⁴ SAE = Serious adverse event. See Section 6.1.1 for definition.

⁵ The study conclusion information in the eCRF is collected once for each subject at the last scheduled visit or at the last follow-up contact for a suspected dengue/**zika/chikungunya** case, should this case occur during the last scheduled visit or earlier if the subject terminates study participation or is lost to follow-up.

⁶ **Symptoms are fever for dengue, Zika and chikungunya, and rash for Zika.**

⁸**The field staff will re-consent at the first opportunity**

Table 3 List of study procedures for expansion cohort subjects (Amended 16 October 2017)

Procedure	Surveillance							Suspected Dengue/Zika/Chikungunya Visits (at hospital/clinic) as applicable		
	Visit 1 # Day 0	Monthly contact between visits	Visit 2	Monthly contact between visits	Visit 3	Monthly contact between visits	Visit 4	First visit Day 0	Return visit ²	Follow-up visit ²¹

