5.5.2.3. Collect blood sample

- A blood sample for serology will be collected from all enrolled subjects (see Section 5.8 for details regarding sample collection). For children <2 years of age, the total amount of blood collected will not exceed 5 mL at any visit.

5.5.2.4. Instruction on enhanced passive dengue, chikungunya and Zika surveillance by the subject or subject's parent(s)/LAR(s) (Amended 16 October 2017)

Study personnel will train subjects/subject's parent(s)/LAR(s) to recognize dengue, *Zika and chikungunya* symptoms and will instruct them to contact the study personnel or come to a designated study hospital/clinic for medical evaluation within 5 days of the occurrence of *fever and/or rash* that may be associated with suspected dengue, *chikungunya or Zika* (defined in Section 5.7.1, 5.7.2 and 5.7.3).

Each household will also be given at least one dengue kit, as applicable, which includes thermometers, study contact information (phone numbers) and an instruction card with information about dengue, *Zika and chikungunya* symptoms. *This card will also provide instructions on who to contact and what to do if any of these infections are suspected.*

Participants or LAR will be instructed on how to take body temperature and how to record the temperatures in a diary log.

See Section 5.6 for details regarding management of suspected dengue, *chikungunya and Zika* cases.

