5.6. Management of suspected dengue, *chikungunya and Zika* cases (Amended 16 October 2017)

All study subjects with suspected dengue, *chikungunya and/or Zika* should be seen at a designated study hospital or clinic by the study physician.

The first visit to the study hospital/clinic will include a detailed clinical examination to assess the subject’s general condition, body temperature, height and weight, cardiac and respiratory rates, blood pressure, dengue, *chikungunya and Zika* associated clinical signs/symptoms and relevant clinical signs/symptoms (e.g., fatigue, headache, pain behind the eyes, abdominal pain, nausea, vomiting, muscle ache, joint ache, diffuse rash, photophobia and pruritus).

A blood sample should be collected by the hospital/clinic for laboratory confirmation of dengue, *chikungunya, Zika and differential diagnosis*. This sample is referred to as the ‘acute’ serum sample. In addition, a blood sample for haematology (CBC and HCT) will be collected (*mandated procedure for subjects presenting within the first 14 days*

following onset of fever and/or rash). If blood chemistry is conducted according to local clinical practice, these data may also be collected.

If dengue, ***chikungunya or Zika*** is still suspected after the first visit to the study hospital/clinic, a return visit for suspected dengue, ***chikungunya and/or Zika*** may be needed and will be conducted as directed by National guidelines by the study physician.

A return visit is a visit linked to suspected dengue, ***chikungunya and/or Zika***, occurring if the evolution of the subject's physical condition necessitates medical evaluation, according to local medical practice. The investigator will determine whether this return visit is necessary and whether it is considered as part of the same episode. If a return visit occurs, the diary log will be verified and possibly used by the physician to complete the clinical symptoms in the eCRF.

Medical data related to any suspected dengue, ***chikungunya and/or Zika*** case will be collected for hospitalized study subjects and for those followed in the outpatient setting at the return visit. Treatment will be given according to local standard routines, following national guidelines.

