Subsequent Yearly Visit(s) as applicable 5 mL whole blood	Yearly	3000 for Visit 4 and 1500 for visit 5 and 6 which applies only to subjects of the wave 1	yes	Dengue IgG ELISA** (only for subjects IgG negative at the previous visit)	250 µL	1	1	1
			yes	Dengue virus 1-4 neutralizing antibodies	1 mL	2	1	2
				YF neutralization			4	
				Zika neutralization			3	
				Zika serology (IgG) #				
			Chikungunya serology (IgG) #	2				
yes	Chikungunya neutralisation	remaining volume	3	1	3			

*tertiary (exploratory) analysis, number of subjects in the subset will be determined during analysis

- not applicable,

** Dengue IgG indirect ELISA

*** Wave 1 enrolment = initial cohort / Wave 2 enrolment = Expansion cohort

Indirect DENV IgG assay is repeated in the following scheduled visits (after enrolment) only if the subject was negative for DENV IgG at the previous scheduled visit. Zika IgG assay is repeated in the following scheduled visits (after enrolment) only if the subject was negative for Zika IgG at the previous scheduled visit; chikungunya IgG assay is repeated in the following scheduled visits (after enrolment) only if the subject was negative for chikungunya IgG at the previous scheduled visit

Table 12 Laboratory read-outs at each time point, and priority ranking for suspected dengue, chikungunya and/or Zika visits for EARLY presenters (Amended 16 October 2017)

SUSPECTED DENGUE, CHIKUNGUNYA AND/OR ZIKA VISITS – EARLY PRESENTERS								
Blood sampling time point		No. Subjects	Subset	Component	Serum aliquot volume	Aliquot priority rank	Test priority rank	Aliquot number
Type of contact/ Amount of whole blood	Sampling time point							
First visit (amount of blood= 5 mL for < 2 years of age and 10 mL for all other subjects)	Sample collected ≤ 5 days of fever and/or rash	unknown	-	Dengue RT-qPCR	750 µL	1	1	1
				Zika and chikungunya RT-qPCR			2	
				Dengue virus 1-4 neutralizing antibodies	750 µL	3	1	2
				Dengue IgM and NS1 ELISA	500 µL	2	1	3
				Zika neutralising antibodies	1 mL	4	1	4
				Chikungunya neutralizing antibodies and Serology for Zika (IgG/IgM) and chikungunya (IgG/IgM)	remaining volume	5	1	5
				Optional for severe cases	PCR	200 µL	-	
First visit (total amount of blood per local practice)	Sample collected before day 14 of onset of fever/rash	unknown		CBC, HCT	No aliquot	-		

CONFIDENTIAL

116606 (EPI-DENGUE-006 BOD BR)
Protocol Amendment 4 Final

SUSPECTED DENGUE, CHIKUNGUNYA AND/OR ZIKA VISITS – EARLY PRESENTERS								

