Blood sampling time point		No. Subjects	Subset	Component	Serum aliquot volume	Aliquot priority rank	Test priority rank	Aliquot number
Type of contact/ Amount of whole blood	Sampling time point							
Suspected dengue follow-up visit (total amount of blood 5 mL)	Approximately 21 days after first visit	unknown	-	Dengue IgM and Dengue capture IgG ELISA	500 µL	1	1	1
				Dengue virus 1-4 neutralizing antibodies	1 mL	2	1	2
				Serology for Zika (IgM/IgG) and chikungunya (IgM/IgG)			2	
				Zika neutralizing antibodies			3	
				Chikungunya neutralizing antibodies	remaining volume	3	1	3

- not applicable

Table 13 Laboratory read-outs at each time point, and priority ranking for suspected dengue, chikungunya and/or Zika visits for LATE presenters

SUSPECTED DENGUE, CHIKUNGUNYA AND/OR ZIKA VISITS – LATE PRESENTERS								
Blood sampling time point		No. Subjects	Subset	Component	Serum aliquot volume	Aliquot priority rank	Test priority rank	Aliquot number
Type of contact/ Amount of whole blood	Sampling time point							
First visit (total amount of whole blood 5 mL)	Sample collected > 5 days or more after fever and/or rash	unknown	-	Dengue IgM and Dengue capture IgG ELISA	500 µL	1	1	1
				Dengue virus 1-4 neutralizing antibodies	1 mL	2	1	2
				Zika and chikungunya RT-qPCR			2	
				Serology for Zika (IgG/IgM) and chikungunya (IgG/IgM)	remaining volume	3	1	3
First visit (total amount of blood per local practice)	Sample collected before day 14 of onset of fever/rash	unknown		CBC, HCT	No aliquot	-		
Suspected dengue, chikungunya and Zika follow-up visit (total amount of blood 5 mL)	Approximately 21 days after first visit	unknown	-	Dengue IgM and Dengue capture IgG ELISA	500 µL	1	1	1
				Dengue virus 1-4 neutralizing antibodies	1 mL	2	1	2
				Serology for Zika (IgG/IgM) and chikungunya (IgG/IgM)			2	
				Zika neutralizing antibodies			3	
				Chikungunya neutralizing antibodies	remaining volume	3	1	3

- not applicable

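### For a child under 2 seen within about 14 days of onset, the first suspected-case visit calls for a 5 mL diagnostic sample plus a mandated CBC/HCT sample, which exceeds the protocol's own 5 mL per-visit limit

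*Protocol*

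**What the plan says.** Children may enrol from 6 months of age (protocol 4.4). Section 5.5.2.3 limits blood taken from the youngest: "For children <2 years of age, the total amount of blood collected will not exceed 5 mL at any visit".

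For the first visit of a suspected case, the laboratory tables in 5.8.2.2 set these diagnostic volumes:

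- Table 12, early presenters: "First visit (amount of blood= 5 mL for < 2 years of age and 10 mL for all other subjects".
- Table 13, late presenters of any age: "First visit (total amount of whole blood 5 mL".

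Haematology is handled separately. Section 5.6 describes the diagnostic sample and continues: "In addition, a blood sample for haematology (CBC and HCT) will be collected". Tables 2 to 4 carry the same requirement as a procedure row, which in Table 2 begins "Blood sample for CBC and hematocrit (mandated for subjects presenting within 14 days following". None of these exempts young children. Tables 12 and 13 give CBC/HCT its own row, with no serum aliquot and no stated volume: "First visit (total amount of blood per local practice".

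The time window is not worded the same way throughout. The synopsis, 5.6 and Tables 2 to 4 refer to presentation within 14 days of onset; the CBC/HCT rows of Tables 12 and 13 refer to a sample taken before day 14. The two differ only for day 14 itself.

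**The concern.** The diagnostic sample alone uses the whole allowance for a child under 2. A second, mandated sample at the same visit then has no volume left to come from. A site cannot take the full diagnostic draw, take the required CBC/HCT and stay within the limit. It must break the limit, shorten the diagnostic draw or omit the blood count, and different sites may choose differently.

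At stake is compliance with a paediatric blood limit that the protocol itself sets, and consistent practice between sites.

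**Working it through.** **Inputs**

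- Limit for under-2s: C = 5 mL per visit (5.5.2.3).
- Diagnostic draw: D = 5 mL for under-2 early presenters (Table 12) and D = 5 mL for all late presenters (Table 13).
- Haematology draw: v mL, with v > 0 and no value stated (Tables 12 and 13).

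The protocol gives no visit total to reproduce, so the check is to add the two draws and compare the sum with the limit.

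**Step 1: the total.** T = D + v = 5 + v, so T − C = v. The limit is exceeded by exactly the haematology volume, whatever that is. For illustration, with assumed volumes:

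| Assumed v (mL) | Total T = 5 + v (mL) | Diagnostic draw that fits the limit, 5 − v (mL) |
|---|---|---|
| 0.5 | 5.5 | 4.5 |
| 1 | 6.0 | 4.0 |
| 2 | 7.0 | 3.0 |

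**Step 2: which visits are affected.** Scheduled visits (Table 11) take 5 mL and no haematology, so T = 5. Convalescent visits (Tables 12 and 13) also take 5 mL and no haematology, so T = 5. For late presenters beyond about day 14 the CBC/HCT is not mandated, so T = 5 unless a site chooses to take one. The conflict is confined to the first suspected-case visit of under-2s who are early presenters (within 5 days) or late presenters from day 6 to about day 14.

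**Step 3: whether the limit reaches this visit.** The sentence stands under the enrolment-visit procedures, but its wording covers every visit. At scheduled visits participants of all ages give 5 mL, so an under-2 limit changes nothing there. The one place where the tables lower a volume for under-2s is the early presenter's first suspected-case draw, from 10 mL to 5 mL. That matches the limit and indicates that it was meant to apply there.

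**Step 4: whether the haematology sample lies inside the 5 mL.** Table 10 specifies whole blood for CBC and hematocrit, while Tables 8 and 9 specify serum for the diagnostic assays. Tables 12 and 13 list haematology in a separate row with no aliquot, and 5.6 introduces it as additional. Nothing says that its volume comes out of the diagnostic 5 mL.

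**The case against.** Four arguments run the other way.

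1. **One sample, not two.** The synopsis can be read as a single draw: "A blood sample for dengue, *Zika* and/or *chikungunya* diagnosis and for haematology (CBC and HCT". It gives no volume, however, and 5.6 and the separate table rows point to a second sample. Even with one needle-stick the volume has to be divided, and no text says how.
2. **Haematology is local clinical work-up, outside the study volumes.** Table 10 assigns it to local laboratories under local practice and says the assays are done as needed when dengue is suspected. That lends the reading some support. But 5.6 and Tables 2 to 4 make the test mandatory within the 14-day window, and the limit is written for total blood, not study serum.
3. **Existing rules already cope.** A site could hold the total at 5 mL and process by the priority ranking in 5.8.2.2. This is the best practical answer, and it is close to the fix below. The ranking, though, applies once a sample is short. It does not reduce the 5 mL that Tables 12 and 13 assign to the diagnostic draw, and it does not place CBC/HCT in the order.
4. **The Study Procedures Manual may settle it.** It may; it is not among the documents reviewed. The protocol states both the limit and the volumes, so they should agree there.

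A reader might also infer that an unlimited haematology tube displaces the RT-qPCR and IgM/NS1 aliquots and so threatens the primary endpoint. The documents do not support that. As the plan is written, the diagnostic draw stays at 5 mL and nothing is displaced. Displacement could arise only if haematology were taken inside the limit, and sizing it would need tube volumes and serum yields that the documents do not give.

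**Conclusion.** The contradiction stands as a minor inconsistency. Two stated rules cannot both be met for under-2s at the first suspected-case visit, up to about day 14 from onset. The conclusion rests on reading the limit as covering every visit and the haematology sample as additional; both follow the more specific text.

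The excess equals the haematology volume, which is not stated, and the number of children concerned is not stated either. The totals of 5.5 to 7.0 mL above are illustrations under assumed volumes. The protocol gives no reason for the limit, so a claim of safety harm would go beyond the documents. No sample-size or precision figure is touched.

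The SAP (2.1) records that the study was to end at the visit after the 2018 dengue season. The remaining practical value lies in correcting the record, checking past draws in under-2s and not reusing the wording.

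**What to change.** Leave the limit in 5.5.2.3 as it is. In 5.6 and in Tables 12 and 13, state that for children under 2:

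- the 5 mL total at the first suspected-case visit includes the CBC/HCT sample;
- haematology uses the smallest paediatric tube the local laboratory accepts;
- the diagnostic draw is 5 mL minus that tube, or 5 mL when no CBC/HCT is taken;
- the diagnostic sample is processed in the existing aliquot priority order, with the unranked optional severe-case PCR last.

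Use one wording of the 14-day window throughout.

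The limit should not be narrowed to study-mandated tests, nor should local-practice chemistry be carved out of it (5.6: "If blood chemistry is conducted according to local clinical practice, these data may also be collected"). Either change would loosen a stated paediatric limit without a reason in the documents.

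**Cost.** A few clauses and table entries, and no new procedure. Lower-ranked aliquots may run short in under-2s: neutralization and Zika/chikungunya serology and, in late presenters, the second-ranked aliquot that also carries Zika and chikungunya RT-qPCR. None of these confirms a dengue case (5.7.1.2). They serve optional tertiary objectives, which SAP 7.4 says will not be analysed.

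The tube must be small because of a risk that belongs to the remedy. The early presenter's top two aliquots need 0.75 + 0.50 = 1.25 mL of serum. With an assumed 1 mL tube the remaining 4 mL must yield 1.25/4 = 31% serum; with an assumed 2 mL tube the remaining 3 mL must yield 1.25/3 = 42%. The sponsor should check the local laboratories' minimum volume before fixing the figure.

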5.5.2.5. Diary log distribution (Amended 16 October 2017)

A diary log will be given to all subjects in the household to be used in the event of suspected dengue, *chikungunya and/or Zika illness*. Diary logs will be distributed at the first scheduled visit and if they are needed, at subsequent visits (if the subject no longer has one, e.g., the previous one was lost or used). A new diary log will be issued by the study staff whenever necessary.

The subject will be instructed to start recording any symptoms, ***including rash*** and body temperature ***at*** any time dengue, ***chikungunya and/or Zika infections are*** suspected. Refer to Section 5.6.1 for details.

5.5.2.6. Recording of serious adverse events related to a study procedure

The subject/subject's parent(s)/LAR(s) will be instructed to contact the study staff should any serious adverse event related to a study procedure occur during the study.

Refer to Section 6.2 for procedures for the Investigator to record SAEs that are related to study participation and for guidelines on how to report these SAEs to GSK Biologicals.

5.5.3. Procedures at subsequent scheduled visits (2-6, as applicable) (Amended 16 October 2017)

- For initial cohort subjects, Visit 2 will occur approximately 6 months after Visit 1 and Visit 3 approximately 6 months after Visit 2. Initial cohort subjects willing to extend their participation to three additional years will be re-consented at Visit 3 (i.e. at the end of study Year 1).
- For expansion cohort subjects, scheduled visits should ideally be performed at yearly intervals, preferably during periods of usually low dengue transmission. Expansion cohort subjects will have at most 4 scheduled visits, depending on the time of enrolment.
- For replacement subjects enrolled in the subsequent study years, scheduled visits should ideally be performed at yearly intervals, preferably during periods of usually low dengue transmission.
- A blood (serum) sample will be collected for serology.

Note: Indirect DENV IgG assay is repeated in the following scheduled visits (after enrolment) only if the subject was negative for DENV IgG at the previous scheduled visit.

Zika IgG assay is repeated in the following scheduled visits (after enrolment) only if the subject was negative for Zika IgG at the previous scheduled visit.

Chikungunya IgG assay is repeated in the following scheduled visits (after enrolment) only if the subject was negative for chikungunya IgG at the previous scheduled visit.

Even if the tests are not repeated, the volume of the blood sample remains unchanged.

- ***Socio-demographic and household information will be updated in eCRF (for e.g. change of home location).***
- Medical and vaccination histories will be updated in the eCRF.
- The investigator will remind the subjects about the procedures in case of signs and symptoms of dengue, ***Zika and chikungunya.***

- A new diary log will be distributed for continued dengue, *chikungunya and Zika* surveillance if needed, and any completed diary logs will be verified, as applicable. Subjects will be asked to contact the study staff in the event of the occurrence of a symptom that may be associated with suspected dengue, *chikungunya or Zika* (see Section 5.7.1.1, 5.7.2 and 5.7.3 for suspected dengue, *chikungunya or Zika* definition).
- The subject will be instructed to start recording any symptoms, *including rash* and body temperature any time dengue, *chikungunya and/or Zika* is suspected. Refer to Section 5.6.1 for details.
- Any SAEs related to study procedures will be recorded.

